6.6. Prior and Concomitant Medications

Prior medications and concomitant medications will be coded using the WHO Drug Dictionary. The number and percentage of participants with prior and concomitant medications will be summarized by treatment group and overall for the ITT Population during the DBVC period by WHO drug class and the WHO drug preferred term. For the OLE period, only concomitant medications will be summarized based on OLE Safety Population.

7. EFFICACY

Appendix A provides a list of data displays. Sample data displays are included in a separate document.

7.1. Efficacy Hypothesis

The primary hypothesis is that in participants with PN, ruxolitinib 1.5% cream BID is superior to vehicle cream BID with regard to the WI-NRS4 response rate at Week 12. Assume *OR* is the common odds ratio between the treatment groups for the proportion of WI-NRS4 responses at Week 12. The following are the primary hypotheses of the study:

- H_0 (null hypothesis): OR = 1
- H_A (alternative hypothesis): $OR \neq 1$

7.2. Efficacy Measures

7.2.1. Worst-Itch Numeric Rating Scale

The WI-NRS is a PRO comprised of a single item rated on a scale from 0 ("No itch") to 10 ("Worst imaginable itch"). Each evening beginning on the day of screening through Week 52 or ET, the participant will assess their worst level of PN-related itch during the past 24 hours on a scale of 0 to 10 in an eDiary.

The WI-NRS score for baseline will be determined by averaging the 7 daily WI-NRS scores before Day 1 (ie, Days -7 to -1) for all by-visit summaries. The by-visit WI-NRS score for postbaseline visits will be determined by averaging the 7 daily WI-NRS scores before the visit day. If 4 or more daily scores are missing (out of the 7), the WI-NRS score at the visit will be set to missing. For all daily WI-NRS-related analyses, baseline will be defined as the last available daily WI-NRS score during the last week prior to Day 1 (ie, Days -7 to -1).

7.2.2. Investigator's Global Assessment

The severity and the activity of PN will be assessed via the IGA-CPG-S and the IGA-CPG-A, respectively.

7.2.2.1. Investigator Global Assessment for Stage of Chronic Prurigo

The IGA-CPG-S is an overall severity rating on a scale of 0 to 4 (see Table 3).

Table 3: IGA-CPG-S

Score	Category	Description: Stage	
0	Clear	No lesions (0 lesions)	
1	Almost clear	Rare palpable pruriginous lesions (approximately 1-5 lesions)	
2	Mild	Few palpable pruriginous lesions (approximately 6-19 lesions)	
3	Moderate	Many palpable pruriginous lesions (approximately 20-100 lesions)	
4	Severe	Abundant palpable pruriginous lesions (over 100 lesions)	

Source: Zeidler et al 2021.

The IGA-CPG-S-TS is defined as an IGA-CPG-S score of 0 or 1 with \geq 2 grade improvement from baseline.

7.2.2.2. Investigator Global Assessment for Activity of Chronic Prurigo

The IGA-CPG-A is an overall severity rating on a scale of 0 to 4 (see Table 4).

Table 4: IGA-CPG-A

Score	Category	Description: Activity	
0	Clear	No pruriginous lesions have excoriations or crusts	
1	Almost clear	Very small proportion of pruriginous lesions have excoriations or crusts (up to approximately 10% of all pruriginous lesions)	
2	Mild	Minority of pruriginous lesions have excoriations or crusts (approximately 11%-25% of all pruriginous lesions)	
3	Moderate	Many pruriginous lesions have excoriations or crusts (approximately 26%-75% of all pruriginous lesions)	
4	Severe	Majority of pruriginous lesions have excoriations or crusts (approximately 76%-100% of all pruriginous lesions)	

Source: Zeidler et al 2021.

The IGA-CPG-A-TS is defined as an IGA-CPG-A score of 0 or 1 with \geq 2 grade improvement from baseline.

7.2.3. Prurigo Activity Score

The extent and severity of PN will also be assessed via the PAS (v1.2). The first 3 items are descriptive of the type, predominant type, distribution, and quantity of pruriginous lesions. The remaining 2 items of the PAS will assess disease activity in terms of percentage (ie, 0%, 1%-25%, 26%-50%, 51%-75%, and 76%-100%) of pruriginous lesions with excoriations/crusts on top (to reflect active scratching) and the percentage (ie, 100%, 76%-99%, 51%-75%, 26%-50%, and 0%-25%) of healed pruriginous lesions in order to quantify change of PN skin lesions. In addition, the total number of pruriginous lesions in a representative area will be identified at screening and followed throughout the study.

7.2.4. Body Surface Area

Total estimation of the %BSA treatment area will be used to determine the number of tubes of study cream dispensed at each visit. Treatment area is defined as the area affected by pruriginous lesions plus an approximate 1-cm area surrounding each lesion. Body surface area assessment will be approximated to the nearest 0.1% using the palmar method as a guide. The palmar method is the palm plus 5 digits, with fingers tucked together and thumb tucked to the side (handprint), which is considered as 1% BSA, and the thumb is considered 0.1% BSA.

7.2.5. Other Patient-Reported Outcomes

Patient-reported outcomes will be assessed at designated visits as outlined in the Protocol.

For all PRO assessments conducted at the study site, in order to avoid bias in the participants' responses to the questionnaires, assessments should be completed before any other evaluations or study procedures on the day of the study visit and prior to treatment-related discussions with the investigator or study site staff.

7.2.5.1. Skin Pain Numeric Rating Scale

Participants will be instructed to complete and record the Skin Pain NRS in a diary each evening, beginning on the day of screening through Week 52 or treatment discontinuation, whichever comes first. The participants will assess their worst level of PN-related skin pain during the past 24 hours on a scale of 0 to 10.

The Skin Pain NRS score for baseline will be determined by averaging the 7 daily NRS scores before Day 1 (ie, Days –7 to –1) for all by-visit summaries. The by-visit Skin Pain NRS score for postbaseline visits will be determined by averaging the 7 daily NRS scores before the visit day. If 4 or more daily scores are missing (out of the 7), the Skin Pain NRS score at the visit will be set to missing. For all daily pain-related analyses, baseline will be defined as the last available daily pain NRS score during the last week prior to Day 1 (ie, Days –7 to –1).

7.2.5.2. Dermatology Life Quality Index

The DLQI is a simple, 10-question, validated questionnaire to measure how much the skin problem has affected the participant over the previous 7 days (Finlay and Khan 1994).

The scoring of each question will be as follows: 3 (very much), 2 (a lot), 1 (a little), 0 (not at all or not relevant).

[figure not shown]
The following imputation will be applied for those questionnaires considered incomplete:

[figure not shown]
- If 1 question is left unanswered, then this is scored as 0; the scores will be summed and expressed as usual (ie, out of a maximum of 30).
- If 2 or more questions are left unanswered, the questionnaire will not be scored.
- For Question 7, the following criteria applies:
 - If answered "yes," then the score will be 3.
 - If answered "no," but then either "a lot" or "a little" is ticked, then the score will be either 2 or 1, respectively.
 - If answered "not relevant," then the score will be 0.
 - If answered "no," but the second half is left incomplete, then the score will remain 0.
- If 2 or more response options are ticked, the response option with the highest score will be recorded.
- If there is a response between 2 tick boxes, the lower of the 2 score options will be recorded.
- For DLQI 6 subscales, if the answer to one question in a subscale is missing, that subscale will not be scored.

The DLQI total score will be calculated by summing the score of each question, resulting in a maximum of 30 and a minimum of 0. The higher the score, the more the quality of life is impaired.

Total DLQI scores are categorized as follows: 0 to 1 (no effect), 2 to 5 (small effect), 6 to 10 (moderate effect), 11 to 20 (very large effect), and 21 to 30 (extremely large effect).

The questionnaire is also analyzed under the following 6 subscales: symptoms and feelings (Questions 1 and 2), daily activities (Questions 3 and 4), leisure (Questions 5 and 6), work and school (Question 7), personal relationships (Questions 8 and 9), and treatment (Question 10).

7.2.5.9. EQ-5D-5L

The EQ-5D-5L is a standardized instrument for use as a measure of health outcome (Herdman et al 2011). The EQ-5D-5L will provide data for use in economic models and analyses including the development of health utilities or quality-adjusted life-years.

The EQ-5D-5L consists of 2 sections: the EQ-5D descriptive system and the EQ VAS. The descriptive system comprises 5 dimensions: mobility, self-care, usual activities, pain/discomfort, and anxiety/depression. Each dimension has 5 levels: Level 1 = no problems, Level 2 = slight problems, Level 3 = moderate problems, Level 4 = severe problems, and Level 5 = extreme problems. The EQ VAS records the participant's self-rated health on a vertical VAS (0-100), on which the endpoints are labeled "the best health you can imagine" (100 score) and "the worst health you can imagine" (0 score).

The categorical outcomes on the 5 dimensions of EQ-5D will be summarized. Additionally, the change from baseline in EQ VAS score will be analyzed.

7.3. Analysis of the Primary Efficacy Parameter

7.3.1. Primary Efficacy Analysis

The primary analysis will be based on the ITT Population in the DBVC period. A summary of the primary endpoint analysis is provided in Table 5.

Table 5: Summary of Primary Analysis

Parameter	Definition	
Treatment	Ruxolitinib 1.5% cream compared with vehicle cream	
Population	ITT Population	
Variable	WI-NRS4 response at Week 12	
Population-level summary	WI-NRS4 response rate difference with 95% CI	

Note: Participants with missing Week 12 data for any reason, including treatment discontinuation (due to development of AD lesions or any other cause), will be defined as nonresponders. No rescue therapy is allowed in this study.

The WI-NRS score at each postbaseline visit (ie, the by-visit WI-NRS score), will be determined by averaging the 7 daily NRS scores before the visit day. If 4 or more daily scores are missing (out of the 7), the WI-NRS score at the visit will be set to missing. Missing WI-NRS scores at each postbaseline visit will be imputed as nonresponders for the primary analysis. The baseline for the by-visit WI-NRS score will be determined by averaging the 7 daily NRS scores before Day 1 (ie, Day -7 to Day -1). The proportion of participants with a WI-NRS4 response, defined as achieving a \geq 4-point improvement in the by-visit WI-NRS score from baseline, will be summarized by treatment group and visit.

The primary hypothesis specified in Section 7.1 will be tested at a 2-sided $\alpha = 0.05$ level using a CMH test stratified by IGA-CPG-S score (2 or \geq 3) and geographic region (North America or outside of North America). The p-value and stratum-adjusted WI-NRS4 response rate difference with the 95% CI will be provided. An overall odds ratio will also be provided with the 95% CI.

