7. DISCONTINUATION OF STUDY TREATMENT AND PARTICIPANT WITHDRAWAL

7.1. Discontinuation of Study Treatment

7.1.1. Reasons for Discontinuation

Participants **must** be discontinued from study treatment for the following reasons:

- The participant becomes pregnant.
- Consent is withdrawn.

Note: Consent withdrawn means that the participant has explicitly indicated that they do not want to be followed any longer; in this case no further data, except data in the public domain, may be solicited from or collected on the participant. Consent may also be partial. Participants may choose to discontinue study treatment and remain in the study to be followed for safety.

- Further participation would be injurious to the participant's health or well-being, in the investigator's medical judgment.
- Unacceptable toxicity as noted in Section 6.5.2.
- Worsening PN and the need for treatment with a prohibited medication as noted in Section 6.6.3.
- Worsening PN during either the DBVC period or the OLE period, in which the extent of PN to be treated (ie, all areas excluding the scalp plus 1 cm surrounding pruriginous lesion[s]) exceeds 20% BSA.
- If a participant is found after randomization not to have met eligibility criteria at the time of enrollment.
- The study is terminated by the sponsor.
- The study is terminated by the local health authority, IRB, or IEC.
- Development of AD lesions.

A participant **may** be discontinued from study treatment as follows:

- If, after 2 consecutive study visits and reinforcement of study cream application by site staff, a participant's cream usage exceeds one 60-g tube every 4 days, a participant who again fails to meet compliance benchmarks at a subsequent visit may be considered for withdrawal from the study. The medical monitor should be consulted for instruction on handling the participant.
- If a participant is noncompliant with study procedures or study cream application in the investigator's opinion, the sponsor should be consulted for instruction on handling the participant.

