8.2. Efficacy Assessments

8.2.1. Worst-Itch Numeric Rating Scale

The WI-NRS is a PRO comprised of a single item rated on a scale from 0 ("No itch") to 10 ("Worst imaginable itch"). Each evening beginning on the day of screening through Week 52 or ET, the participant will assess their worst level of PN-related itch during the past 24 hours on a scale of 0 to 10 in an eDiary (see Section 8.3.1).

An average of the 7-day WI-NRS scores, prior to the baseline visit (minimum 4 out of 7 days' data required), will be used to determine if a participant meets the inclusion criteria. The study staff should contact the participant 1 week prior to each visit to confirm the participant's compliance with completion of the WI-NRS assessment.

Detailed directions for the administration of an eDiary will be provided in the Study Manual.

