8.3. Patient-Reported Outcomes

For all patient-reported outcome assessments conducted at the study site, in order to avoid bias in the participants' responses to the questionnaires, assessments should be completed before any other evaluations or study procedures on the day of the study visit and prior to treatment-related discussions with the investigator or study site staff.

8.3.1. Electronic Diary Assessments: Worse-Itch Numeric Rating Scale and Skin Pain Numeric Rating Scale

Participants will either bring and use their own device or be issued a handheld device (eDiary) at the screening visit. Each participant will be instructed to complete the eDiary each evening beginning on the day of screening through Week 52 or treatment discontinuation. Compliance with the eDiary is calculated electronically in real time via the vendor portal. If the participant is frequently not completing the eDiary, the site staff will be informed so compliance can be addressed in a timely manner. Note: Completion of the WI-NRS a minimum of 4 out of 7 days before study visits is required for the analysis.

Study sites will contact participants 1 week before the baseline visit to confirm compliance with eDiary assessments to ensure information is available to allow randomization if appropriate. The WI-NRS is depicted Section 8.2.1.

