10.4. Statistical Analyses

10.4.1. Primary Analysis

The primary analysis will be based on the ITT population. The baseline WI-NRS score will be determined by averaging the 7 daily NRS scores before Day 1 (Day -7 to Day -1). The by-visit WI-NRS score for postbaseline visits will be determined by averaging the 7 daily NRS scores before the visit day. If 4 or more daily scores are missing (out of the 7), the WI-NRS score at the visit will be set to missing. The proportion of participants with a WI-NRS4 response, defined as achieving a \geq 4-point improvement in WI-NRS score from baseline to Week 12, will be

summarized by treatment groups. Table 14 presents the summary of the primary endpoint analysis.

Table 14: Summary of Primary Analysis

Parameter	Definition
Treatment	Ruxolitinib 1.5% cream compared with vehicle cream
Population	ITT population
Variable	WI-NRS4 response at Week 12
Population-level summary	WI-NRS4 response rate difference with 95% CI

The primary alternative hypothesis (superiority of active ruxolitinib group 1.5% BID compared with vehicle) will be tested at a 2-sided $\alpha = 0.05$ level using a CMH test stratified by stratification factors IGA-CPG-S score (2 or \geq 3) and geographic region (North America or outside of North America). The p-value and stratum-adjusted WI-NRS4 response rate difference with 95% CI will be provided. Overall odds ratio will also be provided with 95% CI. Participants with missing Week 12 data for any reason and participants who develop AD lesions will be defined as nonresponders. No rescue therapy is allowed in this study.

Subgroup analysis by baseline characteristics such as geographic region and any underlying condition known to be associated with the clinical presentation of PN will be performed. In addition, the following sensitivity analyses may be performed, and details will be provided in the SAP.

• Longitudinal logistic regression with repeated measures:

To adjust for the dependence underlying the hierarchical multilevel data structure (visit, participant, and site), a longitudinal logistic regression with repeated measures will be applied. In the model, visits are nested within participants, which are further nested within sites.

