4. Section 5.2, Exclusion Criteria (Exclusion Criterion 4)

Description of change: Extended the window for exclusion of participants with active AD lesions to within 6 months of screening and baseline.

Rationale for change: To minimize the potential for participants with active AD flares, which could confound the assessment of PN-related itch.

5. Section 5.2, Exclusion Criteria (Exclusion Criterion 6g)

Description of change: Added exclusion of participants with an uncontrolled, underlying condition associated with PN.

Rationale for change: Health Authority request.

6. Section 5.2, Exclusion Criteria (Exclusion Criterion 8c)

Description of change: Revised the equation used for estimated glomerular filtration rate from Cockcroft-Gault to CKD-EPI 2021.

Rationale for change: The CKD-EPI has a higher efficacy than Cockcroft-Gault.

7. Section 5.2, Exclusion Criteria (Exclusion Criterion 9); Section 6.6.3, Prohibited Medications and Procedures

Description of change: Added the following prohibited medications with relevant washout periods: opioid antagonists, gabapentin, pregabalin, thalidomide, SSRIs, SNRIs, tricyclic antidepressants, cannabis, cannabinoids, and nonsedating antihistamines used for the treatment of PN.

Rationale for change: Health Authority request and to minimize the potential for confounding efficacy assessments.

8. Section 6.1, Study Treatments Administered; Section 7.1.1, Reasons for Discontinuation; Section 10.4.1, Primary Analysis

Description of change: Participants who develop AD lesions cannot treat AD with the study cream. A participant who develops AD lesions during the study must be discontinued from study treatment, will be considered a treatment failure, and will be defined as a nonresponder.

Rationale for change: Health authority request due to AD possibly confounding efficacy assessments.

9. Section 6.6.1, Permitted Medications and Procedures

Description of change: Clarified that participants may use nonsedating, over-the-counter antihistamines except for the treatment of PN.

Rationale for change: To minimize the potential for confounding efficacy assessments.

10. Section 6.6.1, Permitted Medications and Procedures

Description of change: Removed sedating antihistamines from the list of permitted medications.

Rationale for change: Health authority request.

11. Section 7.1.1, Reasons for Discontinuation

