11.1. Changes to Protocol-Defined Analyses

Coding has been corrected for the FACIT-Fatigue scale. Each item uses a 5-point scale ranging from "0 = not at all" to "4 = very much."

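### SAP 7.3.1 does not carry over the protocol's separate rule that participants who develop AD lesions are nonresponders, and SAP 11.1 declares no change

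*SAP*

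**What the plan says.** Protocol 10.4.1 states: "Participants with missing Week 12 data for any reason and participants who develop AD lesions will be defined as nonresponders". The second group does not depend on missing data. Amendment 3 (Appendix C) introduced this rule and gives the reason: "Health authority request due to AD possibly confounding efficacy assessments".

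The note to Table 5 in SAP 7.3.1 has one subject, "Participants with missing Week 12 data for any reason, including treatment discontinuation (due to development of AD lesions or any other cause"), and makes that group nonresponders. The derivation paragraph below the table says: "Missing WI-NRS scores at each postbaseline visit will be imputed as nonresponders for the primary analysis". Neither it nor the WI-NRS definition in SAP 7.2.1 contains a rule for AD cases whose score is observed.

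SAP 11.1, which lists changes to protocol-defined analyses, has one entry: "Coding has been corrected for the FACIT-Fatigue scale".

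Four other provisions determine which participants are affected:

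- Protocol 7.1.1 lists "Development of AD lesions" among the reasons for mandatory discontinuation of study treatment.
- The itch diary runs "Each evening beginning on the day of screening through Week 52 or ET" (protocol 8.2.1), or "beginning on the day of screening through Week 52 or treatment discontinuation" (protocol 8.3.1).
- Protocol 7.1.2 lets a participant stop treatment and stay in follow-up for safety and efficacy assessments.
- Protocol 8.8 calls for an ET1 visit only when the decision to stop is made before the Week 12/EOT1 visit.

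**The concern.** A programmer working from SAP 7.3.1 would count an AD case with an observed 4-point reduction as a responder. Protocol 10.4.1 counts the same person as a nonresponder. The rule belongs to the primary endpoint, which opens the fixed testing sequence and decides whether the study is terminated after the primary analysis (SAP 3.2 and 10). The same SAP also governs study INCB 18424-320.

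AD during the trial is plausible. Protocol 2.1.2 reports a history of AD in about half of PN patients, and exclusion criterion 4 removes only those with active lesions within 6 months. If the question stays open, it may be settled after unblinding, when the arm of each AD case can be seen.

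**Working it through.** **1. Where the two texts give different answers**

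| Participant with AD | Protocol 10.4.1 | SAP 7.3.1 |
|---|---|---|
| Week 12 average missing | Nonresponder | Nonresponder |
| Average observed, reduction below 4 points | Nonresponder | Nonresponder |
| Average observed, reduction of 4 points or more | Nonresponder | Responder |

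Only the last row conflicts. A participant can reach it in three ways:

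- *AD first found at the Week 12 visit.* The average uses the 7 days before the visit, and treatment and diary ran to the visit, so the score can be fully observed. This is the clear case.
- *AD found 1 to 3 days before the visit.* At most 3 of the 7 scores are lost and 4 remain, which is enough. The case counts only if the ET visit is analysed as Week 12. Protocol 8.8 says that ET evaluations supersede a coinciding scheduled visit, but neither document maps the ET page to Week 12.
- *Earlier AD with continued efficacy follow-up* (protocol 7.1.2). The diary provisions point to missing itch scores after treatment stops, so this route is possible but not planned for.

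**2. The plan's own power figure**

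Inputs from protocol 10.1: 90 per arm, 50% vs 25%, 2-sided alpha 0.05, Fisher exact test, stated power above 90%. Exact enumeration gives 92.3%, so the figure is reproduced. The planned analysis is a CMH test. An unstratified Mantel-Haenszel chi-square on the same inputs gives 94.17%, and this is the reference for step 4.

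**3. Expected number of participants affected**

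Assumptions, none of them in the documents: AD arises in 1% to 5% of each arm over 84 days, onset is uniform, and AD cases respond at the planning rates. The share of AD cases with a usable Week 12 score depends on when AD is recognised:

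- same-day recognition, visit day only: 1/84 = 1.2%
- the 3 preceding days also count: 4/84 = 4.8%
- recognition only at scheduled visits (Week 8, then Week 12): 28/84 = 33%. Unscheduled visits (protocol 8.7) would lower this.

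Let s = AD incidence × share. The expected number reclassified is 90 × s × response rate.

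- Low: s = 0.01 × 1/84 = 0.012%. Ruxolitinib 90 × 0.00012 × 0.50 = 0.005; vehicle 0.003.
- High: s = 0.05 × 28/84 = 1.67%. Ruxolitinib 90 × 0.0167 × 0.50 = 0.75; vehicle 90 × 0.0167 × 0.25 = 0.38.

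The chance that at least one participant is reclassified is 1 − (1 − 0.50s)^90 × (1 − 0.25s)^90. This is 0.8% at the low end and 67.7% at the high end.

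**4. Effect on the conclusion**

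SAP-rule responders X follow Bin(90, 0.50) on ruxolitinib and Bin(90, 0.25) on vehicle. Protocol-rule responders given X follow Bin(X, 1 − s). All outcomes are enumerated, counting significance in favour of ruxolitinib.

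| Incidence × share | s | Power, protocol rule | Any reclassified | Significance lost / gained |
|---|---|---|---|---|
| 1% × 1/84 | 0.012% | 94.16% | 0.8% | 0.009% / 0.005% |
| 1% × 4/84 | 0.048% | 94.15% | 3.2% | 0.04% / 0.02% |
| 1% × 28/84 | 0.33% | 94.05% | 20.2% | 0.25% / 0.13% |
| 5% × 4/84 | 0.24% | 94.09% | 14.9% | 0.18% / 0.10% |
| 5% × 28/84 | 1.67% | 93.58% | 67.7% | 1.02% / 0.44% |

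Adding lost and gained, the chance of a different conclusion is 0.009% + 0.005% = about 0.01% at the low end and 1.02% + 0.44% = about 1.5% at the high end. With AD in one arm only at s = 1.67%, power is 92.73% (ruxolitinib only) or 94.89% (vehicle only).

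**5. A result near the boundary**

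With 22/90 responders on vehicle, 35/90 on ruxolitinib is significant by the unstratified Mantel-Haenszel test and 34/90 is not. One case can therefore decide a borderline result. At the planned effect it cannot: 45/90 vs 22/90 gives Fisher p = 0.0006, and moving 5 ruxolitinib responders (40/90) still gives p = 0.007.

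**The case against.** The strongest reply is that the Table 5 note is a loose condensation of the protocol rule. AD means mandatory discontinuation, discontinuation ends the diary, the score is then missing, and the participant is a nonresponder. By naming AD discontinuation the author seems to have meant to carry the rule over. As a view of intent this is reasonable, and it covers most AD found well before Week 12. It does not settle AD first seen at the Week 12/EOT1 visit: that participant did not stop before the visit and can have a complete diary.

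A second reply is that the protocol sets no time limit on AD. Read literally, its rule would even reach AD in the open-label period, so any cut-off is an addition. This stands, and the fix below labels it as one.

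A third is that the upper figures stack assumptions. A 5% incidence is not from the documents, four weeks of unrecognised AD is a limiting case, and response at the full planning rates is doubtful where AD may confound itch. This also stands, so the figures show that the effect is small and do not estimate it.

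A reader might infer that the SAP deliberately drops the AD rule, or that AD cases in general would count as responders. The documents do not support either reading. The SAP mentions AD in the nonresponder note, and the discontinuation and diary provisions make most earlier AD cases missing at Week 12. The opposite claim, that all earlier AD is nonresponse under both texts, is also too firm, because protocol 7.1.2 allows efficacy follow-up after treatment stops.

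**Conclusion.** Minor, but wrong as written. SAP 7.3.1 omits a separate nonresponder condition that protocol 10.4.1 contains, and SAP 11.1 does not declare the omission. The two texts classify a participant differently only where there is AD, at least 4 of the 7 daily scores before Week 12, and a reduction of at least 4 points.

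Under the stated assumptions, at most 0.75 ruxolitinib and 0.38 vehicle participants are expected to be reclassified, and the conclusion differs with probability of about 0.01% to 1.5%. The direction is unknown because it depends on which arm has the cases. The range leaves out participants who stop for AD early and still supply itch scores; the documents give no basis for their number.

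A reader might also infer a threat to the trial's power. Fisher power does fall to 74.4% if five ruxolitinib responders and no vehicle responders are reclassified, but five is far above the largest expected number here. The sample size and its justification are unaffected. The reason to act is that a primary-endpoint rule requested by a health authority should read the same in both documents before unblinding.

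**What to change.** Before unblinding:

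- **SAP 7.3.1:** state that a participant is a WI-NRS4 nonresponder at Week 12 if the Week 12 score is missing, or if AD lesions are recorded on or before the Week 12 visit, regardless of any observed score. The Week 12 cut-off is an added clarification, since the protocol gives no time limit.
- **SAP 7.4:** state that Overall-TS uses this same WI-NRS4 status. Overall-TS is now derived from the by-visit score, so a change in 7.3.1 alone could make one participant a primary nonresponder and an Overall-TS responder, although Overall-TS requires a WI-NRS4 response. Protocol 10.4.2 calls for a method similar to the primary analysis for the key secondary endpoints.
- **Alternative:** if the narrower rule is intended, declare and justify it in SAP 11.1.

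The cost is a sentence in each of two SAP sections, with no new data and no change in sample size. The downside is that a few participants, in either arm, may move from responder to nonresponder.
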